## 6.12. Summary of analyses by endpoints

The following table summary the analyses done by endpoints described in the previous sections.

**Table 5 List of analyses by endpoints**

	Description of events	Incidence following primary and secondary schedule	Incidence for children < 5 years	Cumulative probability	Analysis of risk factors on IR following primary/secondary schedule	Incidence following:	Analysis of risk factors on IR	Prevalent rate
AESI according to Final diagnosis								
AESI (by MedDRA SOC & PT)	○/●	-	-	-	-	-	-	-
AESI by case definition as listed in CRF	○/●	○	●	○	○*	-	-	-
AESI grouped by body-system	○/●	○	●	-	-	-	-	-
Other AE leading to hospitalization or death according to Final diagnosis								
Other AE leading to hospitalisation or death (by MedDRA SOC & PT)	○/●	-	-	-	-	-	-	-
Other AE leading to hospitalisation or death (Aggregated)	-	○	●	-	-	-	-	-
Meningitis according to Final diagnosis								
Aetiology confirmed meningitis	○/●	○	●	○	○*	-	-	-
Aetiology confirmed, and/or probable meningitis	○/●	○	●	-	-	-	-	-
Probable meningitis	○/●	○	●	-	-	-	-	-
Aetiology Confirmed and/or probable and/or suspected meningitis	○/●	○	●	-	-	-	-	-
Malaria according to Final diagnosis								
Any Malaria	○/●	-	-	-	-	○	○	-
P. falciparum Malaria	○/●	-	-	-	-	○	○	-
Severe Malaria	○/●	-	-	-	-	○	○	-
P. falciparum severe Malaria	○/●	-	-	-	-	○	○	-
Cerebral Malaria	○/●	○	●	○	○*	○	○	-
Death (overall and by gender)								
Death all cause	○/●	○ a	●	○	○*	○	-	-
Death due to an AESI (all grouped)	○/●	○ a	●	○	-	○	-	-
Death due to another AE (all grouped)	○/●	○ a	●	○	-	○	-	-
Death due to meningitis	○/●	○ a	●	○	-	○	-	-
Death due to malaria (including P. falciparum malaria)	○/●	○ a	●	○	-	○	-	-
Death due to P. falciparum malaria	○/●	○ a	●	○	-	○	-	-
Hospitalisation								
Hospitalisation all causes	○/●	○ a	●	○	-	○	-	-
Hospitalisation due to malaria (including P. falciparum malaria)	○/●	○ a	●	○	-	○	-	-
Hospitalisation due to P. falciparum malaria	○/●	○ a	●	○	-	○	-	-
Anaemia								
Anaemia	○/●	-	-	-	-	-	-	○
Severe anaemia	○/●	-	-	-	-	-	-	○
Febrile convulsions								
Febrile convulsions	○/●	○	-	-	-	-	-	-
Surveillance indicator								
Foot positional deformations as a birth defect	○	-	-	-	-	-	-	-
Abscess at the injection site	○	-	-	-	-	-	-	-
● Analysis to be done for AS and EHS			Primary objective					
○ Analysis to be done only for AS			Secondary Safety objective					
* Sensitivity analysis using site as random effect			Secondary other objective					

## 7. STATISTICAL CALCULATIONS

### 7.1. Methodology for computing confidence intervals

Except specify otherwise, all confidence intervals [CI] will be two sided 95% CI computed using the exact method [[Clopper](#), 1934].

The asymptotic 95% CIs for a mean within a group will be calculated when applicable.

### 7.2. Derived and transformed data

Programming specifications for the derivation of data are supporting the SAP.

#### 7.2.1. Age

Age *in days* at time of enrolment in the study will be computed as the difference between the date of enrolment (date of ICF) and the date of birth.

Calendar age will be expressed in months and will be computed based on (the number of days/365.25)\*12.

The age will be categorised as followed:

- 0-5: less than 6 months
- 6-11: from 6 months to <1 year  
1 - <2 years could also be used
- 12-23: 1 - <2 years
- 24-35: 2 - <3 years
- 36-47: 3 - <4 years
- 48-59: 4 - <5 years

#### 7.2.2. Reference date

The reference date is defined as:

- For the 6-12W study group:
  - Date of vaccination for the DTP/HepB/Hib vaccine dose received
  - Virtual vaccination: virtual dose 4 one week before Visit 6 (i.e. Month 20) mimicking study schedule in the subsequent EPI-MAL-003
- For the 5-17M study group (as they do not follow study visits according to EPI vaccine administrations schedule) in order to mimic study procedures in the subsequent EPI-MAL-003, the virtual vaccinations are:
  - Virtual dose 1: one week before first visit (i.e. Month 0)

- Virtual dose 2: one week before Visit 2 (i.e. Month 1)
- Virtual dose 3: one week before Visit 3 (i.e. Month 2)
- Virtual dose 4: one week before Visit 6 (i.e. Month 20).

Note: For the 5-17M 1st DTP group, the first visit (V1) will be at the age of approximately 6 months. In case an event occurred after ICF signature but before V1, the event will not be included in the computation of IR following EPI vaccine or virtual vaccination, but the event will be included in the computation of IR in children <5 years.

### **7.2.3. Date of occurrence**

The dates of occurrence of events are defined as follows depending on the endpoint:

- Suspected or confirmed AESI and meningitis reported at hospital:
  - Onset date of event
- Suspected AESI and suspected meningitis reported during outpatient visit (see section [7.3](#) for worst case allocation sensitivity analysis):
  - Admission date at outpatient visit
- Other AE leading to hospitalisation or death:
  - Onset date of event if AE is the primary diagnosis
  - Admission date at hospital otherwise
- Suspected or confirmed malaria cases:
  - Onset date of event for hospitalised cases
  - Admission date at outpatient visit otherwise
- Death:
  - Date of death reported in study conclusion

### **7.2.4. Time to onset**

For the computation of IR following DTP/HepB/Hib vaccine or virtual vaccination, the TTO will be computed as [the difference between the date of first occurrence of study endpoint (e.g. AESI) and the reference date + 1].

TTO will be expressed in days.

### **7.2.5. Specifics sub-groups**

The following sub-groups of analysis will be derived as:

- Children with haemoglobinopathies, if at any time during the study the condition is reported in at least one of the below sections:
  - Any known pre-existing conditions reported either at visit 1 or during hospitalisation

- Comorbidity factors reported during hospitalisation
- Other diseases reported during hospitalisation with ICD-10 codes = D55.0, D57.X(X=0-8) , D56.X(X=0-9)

***Otherwise, status will be reported as “No”.***

- HIV-positive children, if at any time during the study the condition is reported in at least one of the below sections:
  - Any known pre-existing conditions reported either at visit 1 or during hospitalisation
  - Diagnosis recorded during outpatient visit
  - Risk factors reported during hospitalisation
  - Other diseases reported during hospitalisation with ICD-10 codes = B20-B24

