Further characterisation of a suspected meningitis case will imply performing a lumbar puncture for examination of CSF (and blood culture if feasible) and etiological (bacterial, viral, protozoal or fungal) search with a two-step laboratory approach.

Lumbar puncture will be performed according to routine medical practice. The diagnosis of bacterial meningitis will first be made on site, based on CSF macroscopic and microscopic examinations and blood culture if feasible (first line laboratory results). CSF tests will include selective culture for *Neisseria meningitidis*, *Streptococcus pneumoniae* and *Haemophilus influenza* type b; latex agglutination tests for detection of bacterial antigens (*Neisseria meningitidis*, *Streptococcus pneumoniae* and *Haemophilus influenza* type b), Gram stain, white blood cell counts and cell differentiation and biochemistry testing (protein and glucose). Cryptococcal infection will be diagnosed using Indian ink, for HIV-positive children and those with unknown HIV-status, if feasible.

In addition, an external laboratory based in South Africa (CLS) is contracted to harmonize laboratory procedures, to provide Quality Assessment and Quality Control and to train laboratory technicians in all sites. If needed, GSK will supplement reagents and consumables to ensure that all diagnostic procedures can be conducted according to protocol.

Based on these first examinations, the diagnosis of bacterial meningitis will be made by the physicians in charge of the children, with support from RAFT upon request from the investigators. Job Aids for medical staff and training on standardized diagnosis are put in place in EPI-MAL-002 to improve the sensitivity and specificity of the case diagnosis for all meningitis. Decisions to start treatment of children with suspected meningitis will be based on the medical routine practice, and should not be delayed by the second line laboratory investigations.

All collected CSF samples, regardless of first line testing outcome, will be shipped to a referral second line laboratory based in South Africa (CLS; unique for all sites) for identification of bacterial, viral, protozoal and fungal meningitis using molecular testing such as PCR.

CONFIDENTIAL115055 (EPI-MALARIA-002 VS AME)
Protocol Amendment 7 Final**Final meningitis case ascertainment**

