9.3.3. Patient characteristics and potential confounding variables

9.3.3.1. Recorded in EPI-MAL-002 and EPI-MAL-003

For all enrolled subjects, socio-demographic characteristics, data on access to care and health care seeking behaviour, neighbourhood of residence (urban/rural area), distance from health facilities, use of malaria control intervention at individual level (e.g. use of bednets, indoor residual spraying, seasonal malaria chemoprevention), information on medication intake (including curative antimalarial drugs) during the 14 days preceding onset of symptoms, whether recorded (evidence of prescription) or reported (prescribed without any evidence or self-medicated) will be recorded in the eCRF. Information on medication given as treatment of an AESI, meningitis or malaria, information on medication given for chronic therapy, information on medication administered in anticipation of a reaction to the vaccination, and exposure to environmental hazards such as chemicals will also be recorded. Data on vaccination, more specifically, dates and doses of EPI vaccine administration, as well as data on medical history including co-morbidities (e.g. chronic diseases, such as known HIV infection), or diagnosed congenital

CONFIDENTIAL115055 (EPI-MALARIA-002 VS AME)
Protocol Amendment 7 Final

diseases, such as known hemoglobinopathies, will also be collected. In case of hospitalisation, type of health care facility will be collected.

For children enrolled in enhanced hospitalisation surveillance or hospitalised children in active surveillance, additional information on co-morbidities will be captured such as malnutrition, chronic diseases, known HIV infection status, known hemoglobinopathies.

Of note, the vaccine history will be ascertained for all enrolled subjects through the following channels: individual vaccination cards, vaccination registers at the health care facilities and vaccination data collected during study area census rounds. If any of the sources described here above confirm vaccination, it will be assumed that vaccination has taken place for the analysis.

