14 Mar 2022	Amendment2 Protocol version: Amendment 7 Final (5 May 2020)  Rationale: based on experience of Interim Analysis of EPI-MAL-002, the decision to lighten the final analysis was taken to consider only relevant points and to be compliant with GSK recommendations in terms of number of outputs. 
 
• Section 5.2: adaptation of ELIM-CODE 2501. The elimination code 2501 is applicable for EPI-MAL-002 (5-17 months at 1st DTP) and EPI-MAL-003 (DTP group enrolled at any DTP). In EPI-MAL-003, completion of Enrolment visit procedures should be achieved within a maximum of 10 days after the administration of DTP/HepB/Hib vaccine for the DTP group. By changing the ELIM-CODE 2501 in EPI-MAL-002, the two studies are now aligned.
 
• Section 6.1: deletion of UNK group label for HIV status and haemoglobinopathies
 
• Section 6.4: signs and symptoms, and medical history adapted
 
• Section 6.5: tabulation of tables related to concomitant medications and vaccinations deleted
 
• Sections 6.6 and 6.7: sections related to COVID-19 assessment and protocol deviations added
 
• Section 6.9.2.1: adapted to consider only analysis of confirmed cases for AESI
 
• Section 6.9.2.2: description added of the manual grouping of other AEs
 
• Section 6.9.3.2: final analysis will be done only on confirmed cases according to protocol definition
 
• Section 6.9.3.2: keep only computation of incidence following schedules; IR will only be computed on the top 10 AEs following grouping
 
• Section 6.9.3.3: addition of the date of field implementation of protocol amendment 4
 
• Section 6.10.4: deletion of analysis of risk factors for each MedDRA SOC/PT for AESI and other AEs leading to hospitalisation or death
 
• Section 6.10.7: deletion of computation of IR for surveillance indicator analysis; clarification of surveillance indicator analysis only for AS
 
• Section 6.11.2: deletion of incidence rate and prevalence calculations for deaths attributed to an AE, and logistic regression and cox models for analysis of risk factors
 

Date	Description

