***Otherwise, status will be reported as “HIV-negative children”.***

### **7.2.6. AESI**

As mentioned in Section 6.9.2, confirmed AESI reported at hospitalisation are coded using MedDRA Dictionary and presented by SOC and PT. The coding is based on ICD-10 code reported by the investigator (see [Vaccine study-specific Coding Guidelines](#)).

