### **7.5.3. Covariates**

#### **7.5.3.1. Potential confounding variables**

Patient characteristics and potential confounding variables will be based on the *first home visit or first hospitalisation*.

The category of covariates will be presented in the TFLs template part.

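### HIV and haemoglobinopathy status can first be recorded at the admission that supplies the event, and children with no record are labelled negative, so subgroup event frequencies in active surveillance are biased upward to the extent that earlier capture is incomplete

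*SAP*

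**What the plan says.** SAP 7.2.5 defines two subgroups: "Children with haemoglobinopathies, if at any time during the study the condition is reported in at least one of the below sections", and "HIV-positive children, if at any time during the study the condition is reported in at least one of the below sections".

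- **Sources for both conditions:** "Any known pre-existing conditions reported either at visit 1 or during hospitalisation".
- **Further HIV sources:** an outpatient diagnosis, risk factors noted in hospital, and hospital ICD-10 codes B20-B24.
- **Further haemoglobinopathy sources:** comorbidity factors noted in hospital and hospital ICD-10 codes. There is no outpatient source.

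For all remaining children, "Otherwise, status will be reported as" is followed by *No* (haemoglobinopathy) or *HIV-negative children*. The SAP document history for Amendment 2 records the "deletion of UNK group label for HIV status and haemoglobinopathies", and SAP 6.1 now lists only positive/negative and yes/no.

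Protocol 9.2.7.1.5 collects known conditions at Visit 1. Protocol 9.3.3.1 then adds: "For children enrolled in enhanced hospitalisation surveillance or hospitalised children in active surveillance, additional information on co-morbidities will be captured". Protocol 9.2.7.4.1, on the meningitis work-up, provides for a cryptococcal test "for HIV-positive children and those with unknown HIV-status, if feasible", so the protocol accepts that status can be unknown.

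SAP 6 plans descriptive analysis of AESI, other AEs and meningitis in these subgroups. SAP 6.9.2.1 and 6.9.2.2 take AESI and other AEs as hospitalised cases. Protocol 9.4.2 sends suspected meningitis to hospital for confirmation.

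For the risk-factor models, SAP 7.5.3.1 takes covariates from the "first home visit or first hospitalisation", while SAP 7.5.3.4 describes them as study-entry covariates.

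**The concern.** Two features combine.

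1. **Timing.** A child whose condition was not known earlier can enter the positive group through the same admission that contributes the event. A child with the same condition who is never admitted has fewer chances of being found. Membership of the positive group then depends partly on having been hospitalised.
2. **Default.** Absence of a record is reported as a negative status. For a child who was never tested, the data do not show that.

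Readers of the subgroup tables could not tell higher risk in these children apart from better recording in sick children. SAP 9 sets aside the protocol's missing-data section (9.7.8.1), so nothing later in the plan corrects the default. The overall co-primary rates are not split by status and are unaffected.

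**Working it through.** **What the documents supply.** They give no prevalence, rate or sample size for either subgroup, so there is no plan figure to reproduce. The only number used from them is about 20,000 children in active surveillance at the analysed sites (SAP 2). All values below for prevalence, hospitalisation and capture are assumptions.

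**Notation, for children who truly have the condition**
- h: share hospitalised
- s0: share already recorded through Visit 1 or, for HIV, an outpatient visit, taken as unrelated to later admission
- d: probability that an admission newly records a child not already recorded
- s1 = 1 - (1 - s0)(1 - d): share recorded among the hospitalised

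**Formula.** The share of true positives labelled positive is h·s1 + (1 - h)·s0. Hospital-ascertained events occur only in hospitalised children, who are labelled with probability s1. If d does not depend on the type of event, the event proportion among labelled positives is multiplied by

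s1 / [h·s1 + (1 - h)·s0].

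The SAP rule is a union of sources, so s1 is never below s0. The factor is therefore at least 1. It equals 1 exactly when s0 = 1 or d = 0.

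**Counts for one case.** Assume 2% prevalence, h = 0.20, s0 = 0.5, d = 0.5, and no true effect of the condition.
- True positives: 20,000 × 0.02 = 400, of whom 80 are hospitalised and 320 are not.
- s1 = 1 - 0.5 × 0.5 = 0.75.
- Labelled positive: 80 × 0.75 + 320 × 0.5 = 60 + 160 = 220.
- Hospitalised share among labelled positives: 60/220 = 0.273, against a true 0.20. The factor is 1.36.
- Labelled negative: 19,780, of whom 4,000 - 60 = 3,940 are hospitalised, a share of 0.199.
- Apparent ratio: 0.273/0.199 = 1.37, when the truth is 1.00. A simulation of 2,000 cohorts gave 1.38.
- Using only the records that predate admission: 200 labelled, 40 hospitalised, share 0.20. The simulated ratio was 1.00.
- In this case 180 of the 400 true positives are reported as negative. They barely move the negative group's rate; the distortion sits in the positive group.

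**Range of the factor** over h = 0.1 to 0.4 and d = 0.25 to 0.9:

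| s0 | Factor |
|---|---|
| 0.2 | 1.43 to 3.38 |
| 0.5 | 1.14 to 1.74 |
| 0.8 | 1.04 to 1.20 |
| 1.0 | 1.00 |

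**Why the two conditions differ.** Take h = 0.15, d = 0.8, and Visit 1 recording 30% of positives.
- With Visit 1 alone, as for haemoglobinopathy: s1 = 0.86, and the factor is 0.86/(0.129 + 0.255) = 2.24.
- If outpatient visits record half of those missed, as could happen for HIV: s0 = 0.65, s1 = 0.93, and the factor is 0.93/(0.1395 + 0.5525) = 1.34.

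**The case against.** The strongest reply is that status does not rest on hospital records alone. Visit 1 feeds both flags, and outpatient diagnoses feed the HIV flag. Outpatient visits of active-surveillance children are captured at all facilities until the end of active follow-up (Protocol 9.1, 9.4.2). With good capture there, the factor is close to 1. This stands, and it rules out reading the bias as automatic. It does not remove the concern. In the 6-12 weeks group, Visit 1 falls about a week after the first DTP dose, usually given at 6 weeks of age, and 44 months of active surveillance follow. Haemoglobinopathy has no outpatient source.

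Several stronger readings are tempting, but the documents do not support them:

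- **That the plan computes incidence rates by HIV or haemoglobinopathy status.** The current text promises descriptive analysis, and SAP Table 5 lists no rate by status. Percentages with a labelled subgroup as denominator carry the same bias.
- **That all tables are affected.** Every child in enhanced hospitalisation surveillance is hospitalised, so the contrast does not arise there. The under-5 rates use census denominators, and no split of these by status is described.
- **That these subgroup figures are designated baselines for EPI-MAL-003.** The study as a whole supplies that baseline, but no passage promises a comparison within these subgroups.
- **That the any-time flags enter the risk-factor models.** SAP 7.5.3 does not refer to them. Covariates present in under 5% of children are excluded, so at an assumed 2% prevalence HIV would drop out, and neither condition is on the forced-in list. Some active-surveillance children are enrolled during an admission (Protocol 9.2.1.1), so a first hospitalisation can be study entry. What remains is that 7.5.3.1 and 7.5.3.4 do not clearly agree.

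**Conclusion.** The concern holds in a conditional form. Two parts need no assumption: the default label is unsupported for any child of unknown status, and the rule allows status to be first learned at the event admission.

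The direction also follows from the rule, given that earlier capture is unrelated to later admission: in active surveillance the labelled-positive frequencies are pushed upward or not at all. The size cannot be derived from the documents. It is 1.00 if Visit 1 and outpatient capture is complete or admissions reveal nothing new, and up to about 3.4 under the assumed values above.

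A reader might infer that subgroup rates are inflated by construction. That goes too far, because it ignores the Visit 1 and outpatient sources. The point concerns descriptive subgroup results and their labels, and it is worth correcting before the final analysis because the repair is cheap.

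**What to change.** 1. **SAP 6.1 and 7.2.5:** replace the default *HIV-negative* and *No* with a not recorded/unknown category. Keep negative only where a negative status is actually recorded; the documents do not show whether the CRF holds this.
2. **Active-surveillance subgroup tables:** classify status from records dated before the admission that supplies the event, whether from Visit 1, an outpatient visit or an earlier hospitalisation. Count children identified later as positive only from the date of first report. Show the current any-time definition as a sensitivity analysis, and report how many positives were first identified at an event admission. Restricting status to Visit 1 is not advised, because it would discard valid outpatient diagnoses made before any event.
3. **SAP 7.5.3.1 and 7.5.3.4:** reconcile the two statements so that an admission supplying an event does not define these covariates.

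The cost is SAP wording and re-derivation of two flags from data already collected, with no change to study conduct. The positive subgroups become smaller and their intervals wider.

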***Otherwise, status will be reported as “HIV-negative children”.***

### **7.2.6. AESI**

As mentioned in Section 6.9.2, confirmed AESI reported at hospitalisation are coded using MedDRA Dictionary and presented by SOC and PT. The coding is based on ICD-10 code reported by the investigator (see [Vaccine study-specific Coding Guidelines](#)).

### **7.2.7. Febrile convulsions**

*As per study protocol (section 9.2.5.4), febrile convulsions are those events reported during hospitalisation in AESI sections only (i.e. General Convulsive Seizure) with ICD-10 codes = R56.0.*

***Note: R56.0 reported in section other AE should not be considered as febrile convolution as per protocol case definition.***

### **7.2.8. Management of consecutive visits and/or hospitalisations**

#### **7.2.8.1. AESI, Meningitis and other AE**

For cases reported at hospital, events in one subject with the same preferred term and with the same onset date or onset date + 1 day will be considered as the same event. In such case, they will contribute to several hospitalisations and one event.

*Remarks:*

1. For other AE leading to hospitalisation or death, if the AE is not the primary diagnosis the hospital admission date will be considered (indeed, the onset date is only available for primary diagnosis).
2. For meningitis a worst case allocation is applicable. In case two or more hospitalisations occurred for different protocol definitions of meningitis with the same onset date or onset date + 1, the event considered will be the worst according to the following order (starting from worst):
  - Bacterial confirmed meningitis / Aetiology confirmed meningitis

- Probable meningitis
- Clinically suspected meningitis
- Suspected meningitis without diagnosis done by the site yet (applicable for progress report)
- Suspected meningitis ruled out afterward

3. This rule is applicable if their onset dates are complete.

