### **6.9.2. Co-primary endpoints**

#### **6.9.2.1. AESI**

- Each AESI will first be analysed separately after case ascertainment on confirmed cases (hospitalised cases) classified by MedDRA SOC and PT level and case definition, and grouped by body system overall:
  - According to principal investigator (PI) diagnosis (i.e. after first line laboratory ascertainment or second line laboratory if available) **for progress report (see section 6.9.3.1) and interim analysis**,
  - According to final diagnosis (external expert diagnosis or PI diagnosis if external expert diagnosis not available) **for interim and final analysis**.
- Note: The confirmed AESI cases are those AESI with an available ICD-10 code (i.e. variable ICD-10 code not equal to “Not confirmed”, as per convention in the case report form [CRF] guidelines).*
- AESI will also be grouped by body system as described in table 3 of the protocol:
  - Nerves and central nervous system: Acute Disseminated Encephalo-Myelitis (ADEM), encephalitis, Guillain-Barre Syndrome, Hypotonic Hyporesponsive Episode (HHE), general convulsive seizure
  - Hepato-gastrointestinal and renal system: intussusception, hepatic failure or renal insufficiency
  - Skin and mucous membrane, bone and joints system: juvenile chronic arthritis, Stevens-Johnson syndrome/toxic epidermal necrolysis, Henoch-Schonlein purpura, Kawasaki disease
  - Systemic diseases and haematology: diabetes mellitus type I, thrombocytopenia, anaphylaxis

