### 6.9.2.2. Other AE leading to hospitalisation or death

Other AE leading to hospitalisation or death are those events different from the pre-defined AESI, meningitis and malaria. These AEs classified by MedDRA SOC and PT level for hospitalised cases will be **described**:

- According to PI diagnosis corresponding to the diagnosis at discharge **for progress report (see section 6.9.3.1) and interim analysis**,
- According to final diagnosis (external expert diagnosis or PI diagnosis if external expert diagnosis not available) **for interim and final analysis**.

*PTs will be grouped into medically relevant groups to provide aggregated incidence rates. Indeed, due to the varied reporting terminologies used, some related or similar medical conditions may be counted separately resulting in partial incidence rate calculation (e.g. bacterial pneumonia and pneumonia, iron deficiency anaemia and anaemia). A manual grouping will be done based on a review of all the MedDRA PTs by the Epidemiologists and a Physician.*

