    - From Study continuation
    - From Study conclusion
In case of several migrations/returns, several migration/return dates will be computed. For such subjects, the last contact date will be computed according to migration/return dates.
In case of any inconsistencies regarding the migration/return dates, the return will not be considered and the subject will be censored at the first migration date.
- If the ICF is signed after the first reference date, the individual follow-up period will be computed as the difference +1 between the follow-up end date and the ICF date. The follow-up end date remains the same as for subjects with ICF signed before the first reference date.

When AESI will be grouped, in case of multiple cases for a subject, only the first event will be considered in this analysis.

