#### 6.9.3.3. Incidence in children < 5 years

The IR of each and any AESI, of each and any other AE leading to hospitalisation or death (classified by the MedDRA SOC and PT level) and of aetiology confirmed meningitis will be estimated in all children < 5 years per 100,000 person per year. A 95% CI will be computed per year and overall using an exact method for a Poisson variable.

The numerator will be the number of cases of specified events (i.e. AESI) during the study period (in both AS and EHS grouped) and the denominator will be the person-years contribution of children in all communities < 5 years of age. The denominator will be computed using the census data. A census done at least once a year will provide the total number of children under 5 years.

For example, considering 5 census done between January 2015 and January 2017, a first subject recruited in March 2015 and a last subject recruited in April 2017:

The person-year (PY) will be computed as:

$$PY = N1 \cdot \text{Period1} + N2 \cdot \text{Period2} + N3 \cdot \text{Period3} + N4 \cdot \text{Period4} + N5 \cdot \text{Period5}$$

Contrary to the computation of IR following EPI vaccine or virtual vaccination where only the first event is counted in the numerator, for IR in children < 5 years, in case a subject had more than once the same AESI, all events will be counted in the numerator.

Confidence intervals [CI] will be computed using the exact method [[Clopper, 1934](#)].

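### For the under-5 rate of aggregated other AEs, duplicates are merged only on an identical preferred term, so one illness coded under two terms of the same group counts as two events

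*SAP*

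**What the plan says.** Four parts of the SAP bear on this point.

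- **Duplicate rule (7.2.8.1).** For AESI, meningitis and other AEs reported at hospital, "events in one subject with the same preferred term and with the same onset date or onset date + 1 day" are taken as one event. Remark 1 shows that secondary diagnoses enter as events too: "if the AE is not the primary diagnosis the hospital admission date will be considered". The only cross-category merge in this section is for meningitis: "For meningitis a worst case allocation is applicable".
- **Grouping of other AEs (6.9.2.2, added in Amendment 2).** "PTs will be grouped into medically relevant groups to provide aggregated incidence rates". The reason given is that "some related or similar medical conditions may be counted separately resulting in partial incidence rate calculation". One of its two examples is bacterial pneumonia and pneumonia. The document history lists no matching change to 7.2.8.
- **Under-5 numerator (6.9.3.3).** The numerator is the number of cases in active and enhanced hospitalisation surveillance together. In contrast to the post-vaccination rates, "in case a subject had more than once the same AESI, all events will be counted in the numerator".
- **Scope (Table 5, adapted in Amendment 2).** Under-5 incidence is marked for the aggregated other-AE row and not for the other-AE row by SOC and PT. The text of 6.9.3.3 still speaks of SOC and PT level, but in Table 5 the aggregated rate is the one scheduled.

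**The concern.** Grouping was introduced because the same condition reaches the database under different terms. Once those terms are pooled, they are by the plan's own judgement names for one medical condition. The rule that decides whether two records are the same event should then work at the level of that condition, but it still works at PT level. Two records of one child's illness under two PTs of a group therefore never merge, and the pooled numerator adds them.

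Such pairs can arise in two ways. Protocol 9.2.7.2.10 has the site record a main diagnosis and any secondary diagnoses, so one stay can carry two PTs. A child can also be admitted to a primary care facility and then to a hospital, with one term at each.

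At stake is the level of the grouped under-5 rates. They serve as background for EPI-MAL-003. A rate that depends on how variably a site codes would carry that variation into site comparisons and into the before/after comparison.

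**Working it through.** **1. The plan's own figure.** Protocol Table 7 is the nearest stated figure. Person-years are 11,500 births × 5 age-years × 2 years = 115,000. The exact Poisson limits for d events are LL = χ²(0.025; 2d)/2/PY and UL = χ²(0.975; 2d+2)/2/PY. For d = 25 this gives 21.7 [14.1, 32.1] per 100,000, and for d = 50 it gives 43.5 [32.3, 57.3]. Both match the table, as do the rows for 1 and 5 events.

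**2. The rule applied to records.** Take three children with one illness each and six records in all:

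| Child | Records | Key = PT | Key = group |
|---|---|---|---|
| A | pneumonia day 0; bacterial pneumonia day 0 | 2 | 1 |
| B | pneumonia day 0; pneumonia day 1 | 1 | 1 |
| C | pneumonia day 0; bacterial pneumonia day 1 | 2 | 1 |
| Total | | 5 | 3 |

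The SAP does not say whether duplicates are removed before or after grouping. The order makes no difference: while the key is the PT, children A and C give two events either way.

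**3. Effect on the rate.** Let s be the share of illnesses recorded under exactly two PTs of one group. Then counted events = true illnesses × (1 + s). The documents do not give s, so the values below are assumptions chosen to show a range.

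| s (assumed) | 25 true illnesses: counted | Rate per 100,000 PY [95% CI] |
|---|---|---|
| 0 | 25 | 21.7 [14.1, 32.1] |
| 4% | 26 | 22.6 [14.8, 33.1] |
| 20% | 30 | 26.1 [17.6, 37.2] |
| 40% | 35 | 30.4 [21.2, 42.3] |

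With 50 true illnesses and s = 20%, the count is 60 and the rate 52.2 [39.8, 67.2], against 43.5 [32.3, 57.3]. Illnesses with three or more PTs of one group would add more. For common conditions the interval is narrower, so the same relative bias is larger compared with it.

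**4. Effect on the interval.** If true illnesses are Poisson with mean λ and each counts twice with probability s, the counted total has mean λ(1 + s) and variance λ[(1 − s) + 4s] = λ(1 + 3s). The ratio of variance to mean is (1 + 3s)/(1 + s). It is 1.6/1.2 = 1.33 at s = 20% and 2.2/1.4 = 1.57 at s = 40%. The exact Poisson method assumes a ratio of 1, so the interval is too narrow as well as shifted upward.

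**5. Where the effect does not reach.** The post-vaccination rates in 6.9.3.2 take the first event after each dose. For grouped AESI the section adds: "When AESI will be grouped, in case of multiple cases for a subject, only the first event will be considered". Meningitis classes collapse to the worst class. Malaria has its own 14-day rule in 7.2.8.2. Tables by PT do not add terms together.

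**The case against.** The strongest reply has four parts.

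*The reason for grouping is over-read.* SAP 6.9.2.2 describes a rate fragmented across terms, not one child's illness receiving two terms. This is fair: no document reports double coding within a child, and its frequency could be negligible. But the recording rules allow it, and the stated key then gives the wrong count.

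*The detail may sit elsewhere.* SAP 6.9.3.3 defers the under-5 method to a technical annex of the mock tables, and 7.2 refers to programming specifications. Neither is available, and either might hold a group-level rule. That does not cure a PT key that the SAP itself states.

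*Importance.* Under-5 incidence uses the secondary population (protocol 9.7.5.1, SAP 6.9.1). This stands, and it limits the weight of the point.

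*The sentence on repeat events names AESI.* This also stands. For other AEs the basis is that the same section defines the numerator as a number of cases.

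A reader might also infer that AESI body-system rates are double counted, for example encephalitis with a seizure in one admission. The documents do not support that as a settled error:

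- Annex 5 of the protocol lists seizures among the encephalitis signs, but it confirms a generalised seizure only after a negative aetiological work-up. Encephalitis is not named in that list. SAP 6.9.3.1 restricts the final analysis to confirmed cases.
- Body systems pool distinct diseases, such as hepatic failure with renal insufficiency. Two of these in one child are not duplicates.
- Protocol 9.7.5.2.1 has a first-event rule for composite endpoints and states no under-5 exception. For these groups the two documents are unreconciled.

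**Conclusion.** The point holds for the under-5 incidence of aggregated other AEs leading to hospitalisation or death. Followed exactly, the plan counts one illness twice when it is recorded under two PTs of the same group. The grouped rate is biased upward by the share of illnesses so recorded, and its exact Poisson interval is too narrow.

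The direction is certain wherever such pairs occur; the size is unknown. The 4% to 40% values are assumptions and should not be read as an estimate of inflation. The conclusion rests on Table 5 as the statement of which under-5 rates will be produced, on the numerator being cases and not children, and on no group-level rule existing in the unseen annex or specifications. It does not mean that the main post-vaccination co-primary rates are wrong.

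**What to change.** Add to SAP 7.2.8.1 that, for aggregated other-AE groups, the duplicate rule uses the medical group in place of the PT. Records of one child in the same group then count as one event if they belong to one hospitalisation, or if their onset dates are equal or one day apart. The hospitalisation clause is needed because remark 1 dates a secondary diagnosis by admission and a primary one by onset; with an onset more than a day before admission, a date rule alone would not merge them.

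Do not apply this merge to AESI body-system or any-AESI groups, where it would change what is being estimated. For those, state whether the first-event rule in protocol 9.7.5.2.1 or the all-events numerator in SAP 6.9.3.3 governs the under-5 rate. If it is the latter, list it in SAP section 9 as a change from protocol.

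The cost is one sentence and one changed key in the program, plus the clarification for AESI groups. PT tables stay as they are, and the grouped other-AE rates become slightly lower.
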